5.4 Care Product Accountability

Kit-box (containing study care product) Accountability forms and Lens Foil Logs will be kept by each site. A sample Kit-box Accountability form is shown in Appendix 2.

To monitor care product usage, any remaining unused study solution will be returned to the investigator at Visit 3 (empty, unopened or partially used). The returned kit-boxes will be recorded on the Kit-box Accountability Logs.

5.5 Study Document and Case Report Forms

The following forms will be completed where appropriate:

eCRFs:

- Baseline Visit
- Eligibility Checklist
- Dispensing Visit
- Follow-up Visit (1 week, 1 month)
- Unscheduled Visit
- Adverse Event Form
- Study Exit Form

Additional Forms

- Statement of Informed Consent
- Participant Information Sheet
- Enrolment Log
- Participant Information Guide
- Kit-box Accountability Log
- Source Document Record Label

Any corrections that need to be made to the essential study documents should be neatly crossed through such that the original entry can still be seen, the new entry written in, and the correction initialed and dated.

6 TREATMENT

6.1 Study Product Formulations

The study solutions are to be used in place of habitual contact lens care solutions and will be randomly assigned to the study subjects in labelled kit-boxes.

6.2 Device Administration

The lenses will be used on a daily wear re-usable, monthly or 2-weekly replacement basis, i.e. lenses worn during the day, removed at night and cleaned and stored with appropriate contact lens care products.

The care systems will be used according to the Patient Information Guide.

7 METHODS AND ASSESSMENTS

7.1 Subject Recruitment

Recruitment materials (adverts, letters, etc.) must be approved by the Research Ethics Committee (REC) or Investigational Review Board (IRB). VCR will provide an approved advertisement, letter and telephone script for recruitment purposes. Any changes to these must be submitted back to the REC/IRB via VCR.

The procedures listed below will be conducted on all subjects. Variables must be collected in the order they are listed on the eCRF.

To participate in this clinical study, the Investigator will explain the Statement of Informed Consent to the subject, ensure each subject understands the subject instructions and determine subject eligibility.

The Investigator is required to answer any questions the subject has concerning the study or the information contained in the Statement of Informed Consent and Patient Information Sheet.

A subject is considered enrolled when he or she signs the Statement of Informed Consent. Other study-related may not be activities undertaken prior to obtaining informed consent.

All subjects enrolled should be accounted for, even if they are not dispensed lenses or study product. A signed Statement of Informed Consent constitutes enrolment. After enrolment, a subject is considered active and should be accounted for at every visit until the completion of or discontinuation from the study.

Each site will be expected to enroll approximately 20 subjects, up to a maximum of 24 subjects.

7.2 Study Visits

7.2.1 Visit Schedule

There will be a maximum of four scheduled visits as follows:

Visit 1a: Baseline

Visit 1b: Lens issue (may be combined with Visit 1a)

Visit 2: 1 week follow-up (7 days \pm 3 days) – WT 1-3 hours

Visit 3: 1 month follow-up (30 days \pm 4 days)

A visit schedule form will be supplied to all sites which will list the visit windows and this can assist in arranging visits within the acceptable visit window.

The investigator should confirm with the subject that they are able to attend the follow-up visits within the visit window before enrolling them in the study. If, in extreme situations (sickness, unforeseen circumstances), the subject can only attend outside the visit window, the investigator should discuss with the CRA whether this visit can be considered a scheduled visit.

The 1-week, and 1-month follow-up visits may only take place when the subject attends wearing their lenses. If this is not the case and the subject is not experiencing any problems with their lenses or the study solutions, the appointment will be rescheduled, ideally within the visit window unless they are experiencing difficulty.

7.3 Questionnaire

At the 1 month visit, subjects will be asked a small number of questions about their experience with the study care product. The responses will be entered by the investigator into the eCRF.

7.4 Visit 1a: Baseline

The subjects should attend the first visit wearing their habitual lenses.

If they are not wearing their lenses, reschedule the visit.

The following procedures will be conducted on all subjects:

- i. Allow the subject to read the Participant Information Sheet and Informed Consent and explain the nature, purpose, risks of the study etc. If he/she is agreeable, ask the subject to sign the Informed Consent Form and initial where appropriate. The investigator (or person taking the consent) should also sign the consent form. Provide the subject with a copy and retain the original.
- ii. The subject is assigned with a Subject ID number according to the Enrolment Log. Subjects must be enrolled sequentially. Enter details on Enrolment Log as outlined on the form.

Baseline Measurements and Eligibility:

The following baseline measurements will be recorded on the Baseline eCRF:

- i. Subject demographics (age, sex, medications and associated medical history, allergies)
- ii. Habitual lens comfort (on insertion, during the day and prior to removal, 0-10)
- iii. Symptoms, problems and complaints
- iv. Vision
 - Subjective vision quality: distance (0-10 scale)
 - Monocular high contrast (HC) visual acuity (VA) with CLs (Snellen/logMAR to the nearest letter)
 - Spherical over-refraction (SOR)
 - Monocular and binocular HC DVA with SOR
- v. Wearing times – habitual lenses:
 - Wearing time at visit
 - Typical insertion time
 - Typical removal time
 - Typical time CL comfort deteriorates
 - Maximum wearing time in last month (hrs.)
 - Days worn per week
- vi. Details of habitual lenses and care system:
 - Lens brand
 - Care system brand

- vii. Rewetting drop usage (type and frequency),
- viii. Lens surface characteristics - habitual lenses
 - Lens surface wetting (0-4)
 - Lens deposits (film: 0-4; no. of white spots)
- ix. Lens fit - habitual lenses
 - Centration (0-2)
 - Corneal coverage (Y/N)
 - Post-blink movement (0-4)
 - Tightness on push-up (0-4)
 - Overall fit acceptance (0-4) and reason if Grade 2 or less.
- x. Remove habitual lenses
- xi. Full ocular health
- xii. Monocular spherocylindrical refraction and monocular HC distance VAs (logMAR or Snellen to the nearest letter)
- xiii. Biometry: Horizontal visible iris diameter (HVID), palpebral aperture (PA), keratometry (D/mm)
- xiv. Slit lamp examination
 - Limbal hyperemia (0-4)
 - Bulbar hyperemia (0-4)
 - Stromal edema (0-4)
 - Vascularization (0-4)
 - Palpebral conjunctival hyperemia (0-4)
 - Upper palpebral roughness (0-4)
 - Corneal staining by sector (type 0-4)
 - Conjunctival fluorescein staining by quadrant (0-4)
 - Other findings (0-4)

See Appendix 4 for grading scales and measurement instructions.

- xv. Complete the eligibility checklist

If at this point the subject is found to be ineligible, then complete an Exit eCRF and exit the subject from the study.

If eligible, the subject will be assigned to one of the four lens types allocated to the site and assigned to one of the study solutions.

7.5 Visit 1b: Lens Fitting and Dispensing

The subjects will undergo a trial fit with the randomly allocated study lens type. If the appropriate study lenses are not available, a dispensing visit will be scheduled for another day.

- i. Slit lamp – confirm continued eligibility if on a different day
- ii. Record the parameters of the lenses on the Dispensing eCRF (lens type / lot number, lens parameters, etc.).

The performance of the lenses should be assessed after 10-15 minutes settling time and the following variables will be assessed:

- iii. Subjective comfort (0-10)

- iv. Vision
 - Monocular HC DVA (with CL)
 - Spherical over-refraction (SOR)
 - Monocular HC DVA with SOR
 - Binocular distance VA with CLs (Snellen/logMAR to the nearest letter)
- v. Surface characteristics
 - Lens surface wetting (0-4) and reason if Grade 1 or less.
- vi. Lens fit
 - Centration (0-2)
 - Corneal coverage (Y/N)
 - Post-blink movement (0-4)
 - Tightness on push-up (0-4)
 - Overall fit acceptance (0-4) and reason if Grade 2 or less.

To be successfully dispensed, subjects must show >Grade 2 lens fit acceptance with the trial lens and must be correctable to 6/12 (20/40) (0.30 LogMAR) or better in each eye. Trial lenses must also show >Grade 1 wettability.

Modifications to optimize the lens power will be allowed.

If the lens fit is acceptable, the investigator will issue the care system (Kit-box containing solution, lens case and instructions) that the subject was randomized to, and complete the Kit-box Accountability Log. All kit-boxes must be accounted for, even if they are not dispensed.

- vii. The subject will be instructed to wear the lenses on a daily wear basis (at least 8 hours a day, 6 days per week) until the 1-week follow-up appointment, unless they experience a problem which warrants lens removal. In this case the subject should contact the investigator.
- viii. The investigator or a clinical assistant will review the Participant Information Guide with the subject, which describes the procedures for contact lens wear, lens care, handling, cleaning and disinfecting. Any subject, who does not follow instructions to a degree that, in the Sponsor or Investigator's opinion, jeopardizes the subject's wellbeing or the validity of the study, will be discontinued.
- ix. The investigator will complete the Source Document Record (Appendix 3).

7.5.1 Study Contact Lens Care Products

Eligible subjects will receive a kit-box containing either the test or control multi-purpose solution as indicated during Randomization. The kit-boxes allocated to each subject must be recorded on the Kit-box Accountability Log.

If a subject proves intolerant to any of the products, then the subject will be discontinued and an Exit form will be completed.

7.5.2 Visit 2: 1-week Follow-up

The 1-week follow-up visit will be scheduled 1 week (7 days ± 3 days) from the lens dispensing date. The subject should wear the lenses 1 to 3 hours prior to the appointment. This has been shown to be the time period when solution-induced corneal staining is most evident.⁵ If the subject attends without lenses or with more than 3 hours of lens wear on that day and they are not having any problems with their lenses or the study solution, the visit should be rescheduled, if possible within the visit window.

The following clinical test variables will be recorded on the Follow-Up Visit eCRF:

- i. Wearing times:
 - Days worn since last visit
 - Typical insertion time
 - Typical removal time
 - Typical time CL comfort deteriorates
 - Maximum wearing time since last visit (hrs.)
 - Wearing time today (hrs.)
- ii. Rewetting drop usage (type and frequency)
- iii. Symptoms, problems and complaints
- iv. Subjective assessments
 - Overall comfort on insertion, during the day and prior to removal (0-10)
- v. Vision
 - Subjective vision quality: distance (0-10 scale).
 - Monocular VA (CL, Snellen/logMAR to the nearest letter)
 - Spherical over-refraction (SOR)
 - Monocular HC DVA with SOR
 - Binocular distance VA with CLs
- vi. Lens surface characteristics
 - Lens surface wetting (0-4)
 - Lens deposits (film: 0-4, no. of white spots)
- vii. Lens fit
 - Centration (0-2)
 - Corneal coverage (Y/N)
 - Post-blink movement (0-4)
 - Tightness on push-up (0-4)
 - Overall fit acceptance (0-4) and reason if Grade 2 or less
- viii. Remove lenses and store in sterile saline
- ix. Slit lamp examination
 - Limbal hyperemia (0-4)
 - Bulbar hyperemia (0-4)
 - Stromal edema (0-4)
 - Vascularization (0-4)
 - Palpebral conjunctival hyperemia (0-4)
 - Upper palpebral roughness (0-4)
 - Corneal staining (type 0-4)
 - Conjunctival fluorescein staining by quadrant (0-4)
 - Other findings (0-4)

See Appendix 4 for grading scales and measurement instructions.

Rinse away fluorescein with non-preserved saline.

Re-insert study lenses.

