2.1.2 Safety Hypotheses

The Oté Sensation multi-purpose solution will be non-inferior to the Bausch & Lomb BioTrue solution in terms of:

Corneal staining – type (mean grade, 0-4), a non-inferior bound of 0.5 will be used.

Limbal hyperemia (grade, 0-4), a non-inferior bound of 0.5 will be used.

Bulbar hyperemia (grade, 0-4), a non-inferior bound of 0.5 will be used.

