7.5.3 Visit 3: 1-month Follow-up

The 1-month follow-up visit will be scheduled 4 weeks (30 ± 4 days) from the dispensing date. The subjects should wear the lenses for a minimum of 2 hours prior to the appointment. If the subject attends without lenses or with less than 2 hours of lens wear on that day and they are not having any problems with their lenses or the study solution, the visit should be rescheduled, if possible within the visit window.

The subject will be asked a small number of questions relating to the study care solution.

The same assessments will be followed as at the 1-week visit and will be recorded on the Follow-Up Visit eCRF. At the UK sites (if requested) worn lenses will be retrieved for return to Visioncare Research for *in vitro* analysis.

The kit-boxes containing any remaining study solution will be collected from the subjects. The Kit-box accountability log will be completed and the kit-boxes returned to Visioncare Research at the end of the study.

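### The Visit 2 rescheduling rule enforces the upper end of the 1-3 hour wear window but attaches no action to wear under 1 hour, so staining can be graded before the period the protocol calls most sensitive

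*Combined protocol and SAP*

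**What the plan says.** The 1-3 hour wear target for Visit 2 appears in the synopsis visit schedule, again in section 7.2.1, and as an instruction in section 7.5.2: "The subject should wear the lenses 1 to 3 hours prior to the appointment". Section 7.5.2 gives the reason, calling this the "time period when solution-induced corneal staining is most evident".

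The rescheduling rule that follows begins "If the subject attends without lenses or with more than 3 hours of lens wear on that day". It applies only to subjects for whom "they are not having any problems with their lenses or the study solution, the visit should be rescheduled, if possible within the visit window". Wear of under 1 hour is not mentioned.

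Section 7.2.1 adds a general condition for both follow-up visits, that "follow-up visits may only take place when the subject attends wearing their lenses", with no minimum time.

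The parallel sentence for Visit 3, in section 7.5.3, does carry a lower limit: "If the subject attends without lenses or with less than 2 hours of lens wear on that day". It has no upper limit.

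Corneal staining is a primary safety hypothesis in section 2.1.2: "Corneal staining – type (mean grade, 0-4), a non-inferior bound of 0.5 will be used". Hours of wear on the day of the visit are recorded on the Follow-Up Visit eCRF. The staining model in section 10.2 contains solution, visit, their interaction, site and subject. It has no wear-time term, exclusion or sensitivity analysis.

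**The concern.** Visit 2 is the only visit timed to the interval in which the protocol expects a solution effect on the cornea to show best. The instruction has two ends and the rule that enforces it has one. Followed literally, the rule lets the examination go ahead for a subject who put the lenses in shortly before arriving.

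If staining has not yet developed at that point, grades are low in both arms and a real test-control difference looks smaller than it is. In a superiority trial such dilution works against the sponsor. In a non-inferiority trial it pulls the upper confidence limit down, away from the 0.5-grade margin, and so favours the test product.

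**Working it through.** The documents give no figure to reproduce, so the main check sets the passages side by side for a subject with no lens or solution problems.

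| Wear on arrival at Visit 2 | Within the stated window? | Action in section 7.5.2 |
|---|---|---|
| No lenses | No | Reschedule |
| Above 0, under 1 hour | No | None stated |
| 1 to 3 hours | Yes | Proceed |
| Over 3 hours | No | Reschedule |

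Of the two out-of-window states among subjects wearing lenses, one is caught and one is not.

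The next step is to see whether another section closes the gap.

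- Section 7.2.1 is satisfied as soon as lenses are in the eye.
- Section 7.7 defines an unscheduled visit by the date window, or by a second visit inside it, and not by hours of wear. A short-wear Visit 2 therefore remains a scheduled visit, and the exclusion of unscheduled visits in section 10.2 does not remove it.
- Section 10.2 tests hypotheses on evaluable subjects but gives no definition of the term and no wear-time criterion.
- Section 11.3 would allow short wear to be logged as a deviation, but says nothing about how the grade is analysed.
- Section 7.5.3 shows that the protocol states a lower-limit trigger where it wants one.

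The effect on the result can only be illustrated. Everything in this list except the completer counts and the margin is an assumption.

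- Completers: 20 test and 10 control in each of six lens groups (synopsis), so 6 × 20 = 120 and 6 × 10 = 60.
- Margin: 0.5 grade (section 2.1.2). True difference assumed to sit exactly on it.
- Share f of Visit 2 examinations made before the window: 5%, 10% or 20%, assumed, with zero test-control difference among them.
- Standard deviation (SD): 0.5 or 0.7, assumed.
- Test: one-sided 5%, Visit 2 alone decisive, assumed.

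Standard error (SE) = SD × √(1/120 + 1/60) = SD × 0.158, which is 0.079 for SD 0.5 and 0.111 for SD 0.7.

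Apparent difference = 0.5 × (1 − f). Probability of concluding non-inferiority = Φ(0.5f/SE − 1.645).

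| f | Apparent difference | SD 0.5 | SD 0.7 |
|---|---|---|---|
| 0% | 0.500 | 5% | 5% |
| 5% | 0.475 | 9% | 8% |
| 10% | 0.450 | 16% | 12% |
| 20% | 0.400 | 35% | 23% |

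If the two follow-up visits were averaged with equal weight and Visit 3 were unaffected, the apparent difference would be 0.5 × (1 − f/2), or 0.4875, 0.475 and 0.45, so the dilution halves. If Visit 3 alone decided, the dilution would vanish.

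**The case against.** The lower end of the window is not absent from the protocol. It stands in the synopsis, in section 7.2.1 and in section 7.5.2, and arriving with under 1 hour of wear departs from it. Section 11.3 bars deviations without written approval and requires unexpected ones to be documented. A reader might infer that the protocol endorses such grades as valid Visit 2 data. It does not say so: what is missing is a consequence, not the requirement. Inclusion in the analysis is the default reading only because nothing removes these grades.

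Wear on arrival is also not wear at grading. Section 7.1 requires variables to be collected in eCRF order. In section 7.5.2 the slit lamp examination follows wearing times, symptoms, comfort, vision, lens surface and lens fit, and staining comes late within it. This narrows the exposed group to clearly short wear. Short wear can also be cured by waiting, while excess wear cannot be undone that day, which could explain the asymmetry. The protocol does not give that reason, however, and the Visit 3 sentence does not follow it. The 3-hour limit is itself soft, since rescheduling is qualified and subjects with problems are exempt.

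A reader might take the illustrated rise from 5% to 35% as an estimate of the risk of a false claim. The documents do not support that. They say staining is most evident at 1-3 hours, not that it is absent earlier, and the time course lies in a cited source. The early-attendance rates and SDs are assumed, and the endpoint is an average over five corneal sectors for which no SD is given. Section 10.2 does not say which visit's contrast decides, and it states only an overall 0.05 error rate.

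Nor is staining the main safety endpoint: section 2.1.2 lists it with limbal and bulbar hyperemia and ranks none of them. These objections limit the size of the problem. They do not remove the mismatch between the window and the rule.

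**Conclusion.** The point holds as a minor one. The target window and the rescheduling rule disagree at the lower end, at the only visit timed to detect solution-induced staining, and no other section supplies the missing step or an analysis rule.

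The direction of any bias follows from the protocol's own rationale, on two conditions: that staining differences are smaller before 1 hour, and that a true difference exists. It would then favour non-inferiority on one of three safety endpoints. The size cannot be estimated from the documents. The table of probabilities is an extreme illustration that stacks several unfavourable assumptions, and it should not be read as a forecast. Confidence that the gap would change the trial's conclusion is low.

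**What to change.** Reconcile the rescheduling sentence in section 7.5.2 with the protocol's own 1-3 hour window so that both ends are enforced: wear below the window leads to waiting or rebooking, and subjects with lens or solution problems remain exempt as now. Add an eCRF check on the wearing time already collected at the visit, so that a value outside the window is flagged before the slit lamp step.

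Optionally, pre-specify a supportive table of Visit 2 corneal staining limited to recorded wear of 1-3 hours. It should be labelled supportive because it selects on a post-randomization variable, and because wear is recorded earlier in the visit than staining is graded, so some subjects near the 1-hour limit will be misclassified.

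The cost is a few words in the protocol, one edit check and at most one table. The downside is that a few visits start later or are rebooked. No new data are needed.

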7.5.3 Visit 3: 1-month Follow-up

The 1-month follow-up visit will be scheduled 4 weeks (30 ± 4 days) from the dispensing date. The subjects should wear the lenses for a minimum of 2 hours prior to the appointment. If the subject attends without lenses or with less than 2 hours of lens wear on that day and they are not having any problems with their lenses or the study solution, the visit should be rescheduled, if possible within the visit window.

The subject will be asked a small number of questions relating to the study care solution.

The same assessments will be followed as at the 1-week visit and will be recorded on the Follow-Up Visit eCRF. At the UK sites (if requested) worn lenses will be retrieved for return to Visioncare Research for *in vitro* analysis.

The kit-boxes containing any remaining study solution will be collected from the subjects. The Kit-box accountability log will be completed and the kit-boxes returned to Visioncare Research at the end of the study.

7.5.4 Study Exit

The Study Exit Form must be completed when a subject exits the study. This will occur either at study completion, i.e. at the 1-month visit, or if the subject is discontinued from the study at another time. A Study Exit eCRF must be completed for all subjects who have signed a consent form. The exit date should also be recorded on the subjects named patient notes i.e. the Source Document Record.

At the study Exit Visit the following measurements are taken:

- i. Monocular spherocylindrical refraction.
- ii. Monocular distance high contrast visual acuity (Snellen/logMAR) with spherocylindrical refraction. If VA is 2 or more lines worse than at Baseline, the reason will be recorded on the Study Exit eCRF.

If the subject is being exited without completing the full study schedule, further details need to be recorded on the exit form. This is described in Section 7.6 below.

